4.2. Inclusion Criteria

- 1. Willing and able to provide informed consent.
- 2. Positive SARS-CoV-2 diagnostic test (RT-PCR or validated rapid antigen test) conducted ≤ 5 days prior to randomization. *Note: The test may be obtained locally. A documented historical record of positive result (RT-PCR or validated rapid antigen test) from test conducted* ≤ 5 days prior to randomization is acceptable.
- 3. Mild or moderate COVID-19 with symptom onset ≤ 5 days before randomization and at least one COVID-19 related symptom present at time of screening:
- Mild COVID-19:
 - Symptoms of mild illness with COVID-19, which could include fever, cough, sore throat, malaise, headache, muscle pain, nausea, vomiting, diarrhea, and loss of taste or smell, without shortness of breath or dyspnea
 - No clinical signs indicative of moderate, severe, or critical illness severity
- Moderate COVID-19:
 - Symptoms of moderate illness with COVID-19, which could include any symptom of mild illness or shortness of breath with exertion
 - Clinical signs suggestive of moderate illness with COVID-19, such as respiratory rate ≥ 20 breaths per minute, heart rate ≥ 90 beats per minute; with saturation of oxygen (SpO2) > 93% on room air
 - No clinical signs indicative of severe or critical illness severity
- 4. For females of childbearing potential: agreement to remain abstinent (refrain from heterosexual intercourse) or use adequate contraception during the treatment period and for 30 days after the final dose of study drug.
- 5. Females of childbearing potential must have a negative pregnancy test prior to initiation of study drug.
- 6. Subject must be able to take oral tablet medications.
- 7. Subject is, in the opinion of the investigator, willing and able to comply with the study drug regimen and all other study requirements.
- 8. Subject must be high risk, defined below.
- Age \geq 70 years OR
- Age \geq 55 years with one of the following risk factors:

- Obesity (body mass index [BMI] \ge 30 kg/m²)
- Diabetes mellitus
- Cardiovascular disease (including congenital heart disease) or hypertension (with at least one medication recommended or prescribed)
- Chronic lung disease requiring routine therapy (eg, chronic obstructive pulmonary disease [COPD], moderate-to-severe asthma, interstitial lung disease, cystic fibrosis, pulmonary hypertension)

OR

- Age 50 to 54 inclusive with two of the following risk factors:
 - Obesity (body mass index [BMI] ≥30 kg/m²)
 - Diabetes mellitus

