8.8. Analysis of Exploratory Efficacy Endpoints

The following exploratory endpoints will be examined in both supportive care only and combination antiviral arms.

Time to sustained alleviation or improvement of COVID-19 symptoms

Sustained alleviation/improvement of COVID-19 signs/symptoms is defined as the first occurrence of 4 consecutive days when all symptoms recorded as moderate or severe at study entry are recorded as mild or absent and all symptoms scored mild or absent at study entry are scored as absent. The first day of the 4 consecutive-day period corresponds to the day that the event is achieved. The endpoint will be based on targeted symptoms, which are the 13 symptoms with severities ranging from none to severe in Item 3 of the COVID-19 symptom diary. Subjects who do not achieve the endpoint will be censored according to the following rules:

Case	LOD-3	LOD-2	LOD-1	Last Observed Day (LOD)	Censoring time
1	Not Met	Not Met	Not Met	Not Met	LOD+1
2	Not Met	Not Met	Not Met	Met	LOD
3	Not Met	Not Met	Met	Met	LOD-1
4	Not Met	Met	Met	Met	LOD-2

The cumulative distribution function for time from Day 1 to sustained alleviation/improvement of symptoms will be estimated by Kaplan-Meier methodology and plotted by treatment group. The summary display will include the Kaplan-Meier estimates of proportion achieving the endpoint by day. The analysis will also be carried on subgroups of time from onset of symptoms (<=3 days, > 3days).

Sensitivity analysis will be carried using the same methods for 2 selected subsets of symptoms: 1) runny/stuffy nose, sore throat, cough, feeling hot or feverish, and fatigue; 2) runny/stuffy nose, sore throat, shortness of breath, feeling hot or feverish, headache, and chills; 3) all symptoms from Item 3 of the COVID-19 symptoms diary except fatigue.

Additional subgroup analyses on age group (<65 and >=65), and symptom onset days (<=3 days and >3 days) for time to sustained alleviation of all 13 symptoms will be performed.

Time to self-reported return to usual (pre-COVID-19) health

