Self-reported return to usual health is defined as the occurrence of 4 consecutive days when the response to "Have you returned to your usual (pre-COVID) health?" in question 3 of the COVID-19 symptom diary indicates return to usual health. Analysis and data handling will be the same as that described for the endpoint of time to alleviation or improvement of COVID-19 symptoms. The analysis will also be carried on subgroups of time from onset of symptoms (<=3 days, > 3days).

Proportion of subjects requiring post randomization rescue therapy

Post randomization rescue therapies will be identified by blinded medical review. The number and proportion of subjects requiring post randomization rescue therapy will be tabulated.

Duration and severity of COVID-19 symptom relapse

For subjects who meet the criteria of COVID-19 symptom relapse, duration of relapse will be computed by counting the number of days that the relapse question (i.e., question 4 of the COVID-19 symptom diary) is answered "yes". Severity will be based on the average response to question 1 of the COVID-19 symptom diary during the days where relapse is indicated. Subjects with the last record indicating relapse will have duration of relapse right censored. Kaplan-Meier analysis will be used to summarize symptom relapse duration by treatment group. Severity of symptom relapse will be summarized descriptively. The analysis will also be carried on subgroups of time from onset of symptoms (<=3 days, > 3days).

Proportion of subjects with symptom relapse and viral rebound

The proportion of subjects who meet both the symptom relapse and viral rebound criteria will be compared between the BEM and placebo arms using the same method as in the primary analysis. The analysis will also be carried on subgroups of time from onset of symptoms (<=3 days, > 3 days) and baseline viral load groups (<median, >=median).

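### SAP 8.8 sets no baseline condition for sustained alleviation or return to usual health, so subjects with nothing in the set to alleviate can count as recovered at the start of follow-up

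*SAP*

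**What the plan says.** SAP 8.8 defines sustained alleviation or improvement as four consecutive days on which symptoms moderate or severe at entry are mild or absent and "all symptoms scored mild or absent at study entry are scored as absent". On dating the event: "The first day of the 4 consecutive-day period corresponds to the day that the event is achieved". On the items: "The endpoint will be based on targeted symptoms, which are the 13 symptoms with severities ranging from none to severe in Item 3" of the diary. Loss of taste and loss of smell are separate yes/no items (SAP 11.1) and are not among the 13. The "time from Day 1 to sustained alleviation/improvement of symptoms will be estimated by Kaplan-Meier methodology".

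The same section adds: "Sensitivity analysis will be carried using the same methods for 2 selected subsets of symptoms". Three sets are then listed: one of 5 named symptoms, one of 6, and the full list without fatigue.

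For the other endpoint, "Self-reported return to usual health is defined as the occurrence of 4 consecutive days when the response to" diary question 3 shows return to usual health. Data handling follows the alleviation endpoint.

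Neither definition sets a condition on the Day 1 diary. The mITT-S definition (SAP 6.5.4) adds none. The only diary-based exclusion (SAP 6.8.5) is for subjects with no diary data at all. Entry requires "at least one COVID-19 related symptom present at time of screening" (Protocol 4.2), and loss of taste or smell is among the example symptoms there.

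**The concern.** Time to alleviation should measure how long symptoms take to resolve. A subject with none of the listed symptoms at baseline has nothing in the set to resolve, yet can be recorded as an early success. The share with the event by day, which SAP 8.8 plans to display, would then include a step at the start that has nothing to do with recovery.

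The subset analyses are the more exposed. A subject who enters with muscle pain and diarrhea has none of the 6 symptoms in the second subset. If those 6 stay absent for four days, the subject is alleviated in that analysis while still ill. Return to usual health has its own gap: a subject who answers Yes to question 3 at baseline, and keeps doing so, counts as an immediate return.

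At stake are the reported recovery times and the sharpness of an exploratory comparison.

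**Working it through.** The plan states no figure for these endpoints, so there is none to reproduce.

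**1. The rule applied to test diaries.** Inputs: the two clauses, the four-day run and the event-day rule of SAP 8.8, and the baseline imputation of SAP 6.8.5.

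| Listed items | Event if Day 1 may start the run | Event if the run starts on Day 2 |
|---|---|---|
| None on Day 1, none later | Day 1 | Day 2 |
| None on Day 1, one mild on Days 3–6 | Day 7 | Day 7 |
| None on Day 1, one mild from Day 2 to Day 29 | no event | no event |
| One mild on Day 1, absent from Day 2 | Day 2 | Day 2 |
| All missing on Day 1 (imputed mild), absent from Day 2 | Day 2 | Day 2 |

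The early event needs two things: no listed symptom on Day 1, and all listed items absent throughout the run.

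**2. Whether entry closes the gap.** It does not. The screening symptom may be of any type, may lie outside the 13 items (taste, smell) or outside a subset, or may have gone by the Day 1 diary, up to 24 hours later (Protocol 6).

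**3. How many subjects.** Let f be the share with no listed symptom on Day 1. The documents do not give it. Assume prevalences of runny nose .45, stuffy nose .50, sore throat .45, cough .65, feverish .40, fatigue .60, breathlessness .15, headache .50 and chills .30. With independent items:

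- Subset 1: f = .55 × .50 × .55 × .35 × .60 × .40 = 1.3%
- Subset 2: f = .55 × .50 × .55 × .85 × .60 × .50 × .70 = 2.7%

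With between-item correlation up to 0.3 in a latent-normal model, f rises to about 7% and 11%. No value was derived for the 13-item set, where f should be smaller.

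**4. Dilution.** Let q be the share of those subjects who stay free of listed symptoms for the run. Early events per arm = f × q. With f from 1% to 10% and q from 50% to 100%, that is 0.5% to 10%, or about 5 to 105 of 1050 (2100/2, SAP 4.3.1). A true 10-point difference among the other subjects appears as 10 × (1 − fq), that is 9.95 down to 9.0 points.

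**5. Median and power.** Assume exponential recovery, placebo median 10.5 days, hazard ratio 1.13, follow-up to Day 26, one-sided 0.025, and q = 1, which is the worst case.

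- Rate λ = ln 2/10.5 = 0.0660. Reported placebo median = ln[2(1 − f)]/λ: 10.5 days at f = 0, 9.7 at 5%, 8.9 at 10%.
- Event probability by Day 26: placebo 1 − exp(−1.716) = 0.820; BEM 1 − exp(−1.939) = 0.856. Sum = 1.676.
- Events among the other subjects: D = 1050(1 − f) × 1.676.
- With exclusion: mean Z = ln(1.13) × √(D/4).
- Under the present rule the early events add variance but no signal: mean Z = ln(1.13) × (D/4)/√[(D + 2100f)/4].
- Power = Φ(mean Z − 1.96).

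| f | D | Present rule: mean Z, power | With exclusion: mean Z, power | Gain |
|---|---|---|---|---|
| 1% | 1743 | 2.536, 71.8% | 2.551, 72.3% | 0.5 |
| 5% | 1672 | 2.424, 67.9% | 2.499, 70.5% | 2.6 |
| 10% | 1584 | 2.286, 62.8% | 2.432, 68.2% | 5.4 |

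A simulation with 3,000 replicates under the same assumptions gave 68.9% against 72.1% at f = 5%, and 63.8% against 70.0% at f = 10%: gains of 3.2 and 6.2 points. The Monte Carlo standard error is √(0.69 × 0.31/3000) = 0.8 points for each power, so about 1.2 for a difference. The two methods agree within that error.

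**The case against.** The strongest reply is that the gap is narrow and its consequence slight. Every subject had a COVID-19 symptom at screening within a day of dosing. Missing baseline symptoms are imputed as mild, and missing usual health as No, so missing data do not create these cases. The main analysis covers 13 items, and the still-ill example arises only in a sensitivity subset. Both endpoints are exploratory and outside the testing sequence of SAP 8.5. SAP 8.8 names no test for alleviation. Protocol 8.3 mentions the log-rank test for time-to-event endpoints in general, but Protocol 8.3.3 has the additional endpoints summarized descriptively. All of this stands, and it limits the severity. It does not supply the missing baseline condition.

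A reader might go further in four ways that the documents do not support:

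- That the endpoint is met vacuously. Only the moderate/severe clause is empty for such a subject; the listed items must still be absent on four consecutive days.
- That the event necessarily falls on Day 1. SAP 8.1 says efficacy is evaluated after treatment, and the Day 1 baseline diary is completed before dosing (Protocol 6.7). SAP 8.8 does not say whether that diary may start the run.
- That having no listed symptom also meets return to usual health. That endpoint rests on question 3 alone.
- That the loss is the fall in power from f = 0 with all 1050 per arm. That is not the relevant comparison, because excluding the affected subjects also reduces the sample.

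**Conclusion.** The point holds as a gap of low severity. SAP 8.8 lets subjects with no listed symptom at baseline, or already at usual health by their own report, count as recovered on Day 1 or Day 2. Because the condition concerns pre-dose status in randomized, blinded arms, the effect should be equal in both: it shortens reported recovery times and weakens the comparison a little, and it is not expected to favor BEM. The power that exclusion would recover is under 1 point at f = 1%, about 3 points at 5%, and up to about 6 points at 10%. Those figures rest on an assumed f, assumed recovery times and hazard ratio, every affected subject staying symptom-free for the run, and use of a log-rank test. The two short subsets are the stronger case; for the 13-item set the effect may be negligible. No primary or secondary conclusion changes.

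**What to change.** In SAP 8.8:

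- Restrict each alleviation analysis (the 13-item set and each subset separately) to subjects with at least one symptom in that set graded mild or worse on the Day 1 diary, after the imputation in SAP 6.8.5.
- Restrict return to usual health to subjects with No to question 3 at baseline, after the same imputation.
- State that the four-day run starts no earlier than the first post-dose diary day, in line with SAP 8.1.
- Tabulate the excluded subjects by arm for each analysis.

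The restriction uses pre-dose data only, so the randomized comparison is preserved within the restricted group. The cost is SAP wording, one baseline flag per analysis, and slightly fewer subjects in these exploratory analyses. It should be settled before unblinding.

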8.3. Statistical Methods

The primary and secondary efficacy analyses will be conducted using the mITT-S population. Efficacy analyses will be repeated using the mITT-C population.

Safety analyses will be performed on the safety population, which consists of all subjects who received at least one dose of study drug. In all safety analyses, subjects will be grouped according to the treatment that the subjects actually received rather than the treatment assigned at randomization. Here, treatment will be considered as BEM monotherapy and placebo for subjects in the supportive-care-only population and as BEM combination and compatible antiviral in the combination antiviral population.

Demographics and baseline characteristics will be summarized by treatment group and overall for each analysis population. Disposition, with respect to both treatment and study completion, will be summarized by treatment group and overall with reasons for discontinuation tabulated.

For continuous variables, descriptive statistics will include the following information: the number of patients reflected in the calculation (n), mean, standard deviation, Q1, median, Q3, minimum, and maximum. For categorical or ordinal data, frequencies and percentages will be displayed for each category.

Time-to-event endpoints will be analyzed using Kaplan-Meier methods for estimation and log-rank test for treatment comparison.

Data handling for quantitative data that are reported as less than the lower limit of quantification, as well as values reported greater than the upper limit of quantification, will be described in the SAP.

In general, data will be considered as observed, ie, values for missing data will not be imputed.

The primary analysis will occur when all randomized subjects have had sufficient follow-up time to complete the Day 29 visit. Data collected during the extended FU period will be summarized separately, after the primary study analysis.

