6.8.5. Missing COVID-19 symptom diary assessment

If a subject was missing all symptom diary assessments, this subject will be excluded from analysis. For the time-to-event analyses, missing individual symptom assessments at times will be imputed prior to statistical analysis. If there is missing data between two assessments, the missing data will be imputed as the worst outcome of the two. Missing data after the last recorded assessment will not be imputed; instead censoring may be utilized for the time to event endpoint in cases where the endpoint was not achieved. For time to sustained alleviation/improvement of symptoms, censoring will be applied thus:

- if the last observed time point does not meet alleviation/improvement criteria, the result is censored at the time of the last recorded result
- if the last observed time point meets alleviation/improvement criteria but the requirement for sustainment (i.e. criteria not maintained over 4 day period) has not yet been met, the result is censored using the approach described in Section 8.8.

Missing baseline assessments will be imputed according to the following rules: 1) missing individual symptoms and worst severity of COVID-19 symptoms will be imputed as 'mild'. 2) Missing assessments for "loss of taste" and "loss of smell" will be imputed as 'no'. 3) Missing general physical health will be imputed as "fair". 4) Missing returned to usual health will be imputed as "no". 5) Missing symptom relapse will be imputed as "not applicable".

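### The censoring table for sustained symptom alleviation keeps every non-achiever at risk beyond the last day the diary can settle, so the Kaplan-Meier curves run low whenever diaries stop early; one case also contradicts SAP 6.8.5

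*SAP*

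**What the plan says.** SAP 8.8 defines sustained alleviation or improvement as the "first occurrence of 4 consecutive days when all symptoms recorded as moderate or severe at study entry are recorded as mild or absent", with symptoms that were mild or absent at entry having to be absent. It dates the event backwards: "The first day of the 4 consecutive-day period corresponds to the day that the event is achieved".

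It then states "Subjects who do not achieve the endpoint will be censored according to the following rules", followed by a four-row table. The first row reads "1 Not Met Not Met Not Met Not Met LOD+1" and the second "2 Not Met Not Met Not Met Met LOD". The third and fourth rows censor at LOD-1 and LOD-2 for subjects two and three days into a qualifying run.

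SAP 6.8.5 covers the same ground. Its first bullet says "if the last observed time point does not meet alleviation/improvement criteria, the result is censored at the time of the last recorded result". Its second bullet sends only subjects who are part-way through a run to the table in 8.8.

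For time to return to usual health the rule is carried over: "Analysis and data handling will be the same as that described for the endpoint of time to alleviation or improvement of COVID-19 symptoms". SAP 8.8 plans Kaplan-Meier curves by arm and daily proportions. Its sensitivity analyses for the symptom endpoint change the set of symptoms, not the censoring. Protocol 8.3 says in general terms "Time-to-event endpoints will be analyzed using Kaplan-Meier methods for estimation and log-rank test for treatment comparison".

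**The concern.** Kaplan-Meier estimation assumes that, on each day, the subjects counted as at risk could have been seen to have the event that day. It also assumes that the time of leaving the risk set says nothing about the outcome. A rule that reads the censoring day off the subject's status at the end of the diary breaks both assumptions, even if the diary stopped for reasons unrelated to symptoms.

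The shape and median of the symptom curves are at stake, together with their sensitivity sets, their subgroups and the return-to-usual-health curves. If the arms stop diaries at different rates, a spurious difference appears between them.

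There is also a programming problem. A subject who does not meet the criteria on the last observed day has two different censoring days in the same SAP.

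**Working it through.** **Inputs from the documents.** Event on the first day T of a 4-day run; the case table; the conflicting bullet in 6.8.5; daily diaries on Days 1-29; Kaplan-Meier by arm. The documents state no figure for this endpoint, so there is none to reproduce.

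**Assumptions.** Diaries stop at random with constant daily probability h. The symptom process is a daily two-state (met / not met) chain. A subject censored on day t counts as at risk on day t.

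**Step 1. The last day a diary can settle.** An event on day T needs qualifying entries on T to T+3, so T+3 ≤ LOD, that is T ≤ LOD-3.

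**Step 2. Compare the table with that day.**

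| Status at end of diary | SAP 8.8 | Days beyond LOD-3 |
|---|---|---|
| Not met on last day | LOD+1 | 4 |
| 1 day into a run | LOD | 3 |
| 2 days into a run | LOD-1 | 2 |
| 3 days into a run | LOD-2 | 1 |

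Under 6.8.5 the first row would be LOD, 3 days beyond.

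**Step 3. Size by hand.** Take day t. A diary ending on t-1, t, t+1 or t+2 cannot confirm an event on day t, yet an unrecovered subject with such a diary is in the table's risk set that day. Of the diaries that run to at least t-1, a share (1-h)^4 run to t+3. The estimated daily hazard is therefore roughly the true hazard times (1-h)^4, and the estimated event-free proportion is roughly S^((1-h)^4). This ignores the earlier exit of mid-run subjects whose run would have broken.

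In the simulated base case, true alleviation is 67.5% at Day 14, so S = 0.325. At h = 1% per day, 0.99^4 = 0.9606 and 0.325^0.9606 = 0.340. Estimated alleviation is 66.0%, an error of about -1.5 points. With LOD for the first row (6.8.5) the exponent is 0.99^3 = 0.9703, and the error is about -1.1 points.

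**Step 4. Simulation.** 1,000,000 subjects per scenario, true median Day 9, true alleviation 54.3% at Day 10 and 67.5% at Day 14. Errors under the SAP 8.8 table, in percentage points:

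| Stopping per day | Day 10 | Day 14 |
|---|---|---|
| 0.5% | -0.72 | -0.73 |
| 1% | -1.45 | -1.47 |
| 2% | -2.86 | -2.94 |
| 4% | -5.71 | -6.02 |

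At 1% per day the estimated median moves from Day 9 to Day 10. Other rules at 1% per day, Day 14:
- LOD for the first row, per 6.8.5: -1.12.
- LOD for everyone: -1.24.
- LOD-3 for everyone: 0.00.

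Across four recovery patterns (true medians Day 6 to 11), the Day 14 error at 1% per day was -1.1 to -1.5. LOD-3 was within 0.1 point at Days 10, 14, 21 and 26 throughout. With no early stopping every rule is exact through Day 26. After that no new event can be confirmed, the curve is flat, and the Day 29 value is 0.7 to 3.2 points low under any of these rules.

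**Step 5. Between arms.** With 2% per day in both arms, a true 15.7-point Day 14 difference between two recovery patterns changes by about 0.4 point. With no true difference but 1% versus 2% per day, the spurious Day 14 gap is 2.94 - 1.47 = 1.47 points.

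A one-sided 2.5% log-rank test under the null, 1050 per arm, gave these error rates under the table (ranges over repeated simulations with different assumed symptom processes). Total stopping over 28 days is 1-(1-h)^28.
- 1% per day in both arms: 2.7%.
- 0.5% versus 1% per day (13% versus 25% of diaries stopped): 6.3-7.4%; with LOD-3, 2.8-3.0%.
- 0.5% versus 2% per day (13% versus 43%): 20.4-22.5%; with LOD-3, 2.3-2.5%.
- 5.5% versus 10.6% of diaries stopped in total: 3.7%.
- 2.8% versus 5.5% in total: 2.5%.

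**The case against.** The table is not arbitrary. In each row it censors at the earliest day on which a qualifying run could still begin, a recognisable convention for saying that the event was not achieved before that day. Gaps inside the diary are imputed, so only terminal stopping matters. If about 5% of diaries stop in total, the Day 14 error is only about 0.3 point. This all stands, and it limits the size of the bias. It does not remove it, because the day a run could begin is not the last day on which an event could have been recorded.

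A reader might infer that the table takes subjects in mid-recovery out too early. It does so only relative to unrecovered subjects. Measured against LOD-3, nobody leaves early and all four cases leave late. Moving mid-run subjects forward to LOD would not cure the bias (Step 4).

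A reader might also infer that a planned symptom test has a false-positive rate of 7% or 20%. The documents do not support that. SAP 8.8 lists no log-rank test for these endpoints. SAP Table 4 names one only for time to hospitalization or death. Protocol 8.3.3 foresees descriptive summaries, with any testing documented in the SAP. Only the general sentence in Protocol 8.3, repeated in the synopsis, would bring a test in. The large error rates also need a marked imbalance in stopping between blinded arms, which nothing in the documents suggests.

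Finally, LOD-3 corrects only the bias that the rule itself creates. Stopping related to symptoms, such as through hospitalization or death, remains a separate problem.

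**Conclusion.** The point holds as a minor one. The censoring table makes recovery look slower than it is, whatever the reason diaries stop, by about 1.5 points at Day 14 per 1% of diaries stopping per day. The stopping rates and symptom patterns are assumptions. The direction follows from the definition of the event and needs no simulation. If nearly all diaries run to Day 29, the effect before Day 27 is negligible.

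The comparison between arms is almost unaffected by equal stopping. It is distorted by unequal stopping, and a log-rank test would be inflated if one were run. Both symptom time-to-event endpoints are exploratory and lie outside the testing sequence in SAP 8.5, so neither the primary analysis nor any multiplicity-controlled claim is touched.

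The conflict between 6.8.5 and 8.8 over subjects not meeting the criteria on the last day is a plain inconsistency and needs resolving in any event. The table also omits patterns such as three qualifying days followed by a non-qualifying last day. The simulations treated these as the first row.

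**What to change.** Replace the case table in SAP 8.8 and the first censoring bullet in SAP 6.8.5 with one rule: every subject without the event is censored at LOD-3, whatever the status on the last days. That is Day 26 for a complete diary. Diaries ending on Days 1-3, for which LOD-3 is zero or negative, are censored at time 0. The second bullet of 6.8.5 should then point to the same rule.

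Report the curves through Day 26 and apply the rule to time to return to usual health. State in 8.8 whether a log-rank test will be run for these endpoints, so that the general protocol sentence is not left to interpretation.

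The cost is a change of SAP wording, one derivation line and a slightly shorter nominal follow-up. No new data are needed, and with complete diaries the estimates through Day 26 do not change.
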